9.3.2 Missing Dates for Efficacy Endpoints

For time-to-event endpoints (Progression Free Survival, Overall Response and Duration of response), if the date is completely missing, no imputation will be performed.

However, the incomplete/partial dates will be handled following the general conventions as detailed in Section 9.3.1.

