9.3 Handling of Missing Data

9.3.1 Missing Dates for Adverse Events and Concomitant Medications

Adverse events and concomitant medications with completely or partially missing assessment dates will have imputation performed as explained below for the purposes of calculation of durations or relativity to study medication.

For the end of a concomitant medication or adverse event:

- **If only Day of end date is missing:**

The last date of the month and year reported or the date of the final contact with the subject, whichever is earlier, will be used as the end date.

- **If Day and Month of end date are missing:**

The last date of year i.e. December 31 of the year reported or the date of the last study contact with the subject, whichever is earlier, will be used as the end date.

- **If Year of end date or complete end date is missing:**

If the year of end of medication/event is missing or end date is completely missing, then no end date will be imputed.

For the start of a concomitant medication or adverse event:

- **If only Day of start date is missing:**

- If the start year and month of medication/event are the same as that for the first dose date, then following approach will be used:

- If the end date of medication/event is NOT before the first dose date or end date of medication/event is completely missing, then impute the start day as the day of first dose date
- Otherwise, impute the start day as 1.

- If the start year and month of medication/event are NOT same as that for the first dose date, then

- Impute the start day as 1.

- **If Day and Month of start date are missing:**

- If start year of medication/event is same as first dose year, then following approach will be used:

- i. For medication, impute the start Month as January and the Day as 1
- ii. For adverse event,

- If the end date of event is NOT before the first dose date or end date of event is completely missing, then impute the start Month and Day as the Month and Day of first dose date;
- Otherwise, impute the start Month as January and the Day as 1.

- If start year of medication/event is NOT same as first dose year, then

- Impute start Month as January and the Day as 1.

- **If Year of start date or complete start date is missing:**

If the year of start of medication/event is missing or start date is completely missing, then no start date will be imputed.

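### Partial progression, response and death dates are imputed with adverse-event and medication rules that ignore known efficacy dates, so individual PFS and DoR values can be wrong or negative

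*SAP*

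**What the plan says.** SAP 9.3.2 has two sentences. On completely missing dates: "For time-to-event endpoints (Progression Free Survival, Overall Response and Duration of response), if the date is completely missing, no imputation will be performed". On the rest: "the incomplete/partial dates will be handled following the general conventions as detailed in Section 9.3.1".

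Section 9.3.1, to which it points, covers adverse events and concomitant medications, and its stated purpose is to compute durations and timing relative to study drug. Its branches are:

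- **Start, day missing, month of first dose:** "end date of medication/event is completely missing, then impute the start day as the day of first dose date". A progression or death has no end date, so this branch would apply to it.
- **Start, day missing, any other month:** "impute the start day as 1".
- **Start, day and month missing, year of first dose:** for an adverse event with no earlier end date, "then impute the start Month and Day as the Month and Day of first dose date". For a medication, "For medication, impute the start Month as January and the Day as 1".
- **Start, day and month missing, another year:** "Impute start Month as January and the Day as 1".
- **End, day missing:** "The last date of the month and year reported or the date of the final contact with the subject, whichever is earlier".
- **End, day and month missing:** 31 December of the reported year or last contact, whichever comes first.

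SAP 9.3.3 gives diagnosis and prior-therapy dates a rule of their own. Efficacy dates have none. SAP 10.5.3 (DoR) and 10.5.5 (PFS) provide censoring only for patients without progression or death.

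**The concern.** A progression, response or death is a single dated event. It is not the start or end of an episode, and it is neither an adverse-event record nor a medication. The start rule for adverse events leans towards classing an event as treatment-emergent, which is sensible for safety. Applied to progression, it pulls the event towards first dose. The end rule pushes it the other way. None of the branches checks the result against the last progression-free scan, the documented response or the last date known alive.

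Two programmers could both follow the SAP and report different PFS and DoR values for the same patient, and some of those values would be impossible. DoR is part of the primary objective. SAP 10.5.3 summarises it by mean, standard deviation, median, minimum and maximum, several of which respond directly to one bad value.

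**Working it through.** **Plan's own figures.** Neither 9.3.1 nor 9.3.2 states a number to reproduce. The two-stage design does reproduce. Summing P(X1 = x) × P(X2 ≥ 31 − x) over x = 9 to 20, with X1 from 20 and X2 from 41 patients, gives 0.0487 at a 40% response rate and 0.904 at 60%. No date enters that calculation.

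**Inputs.** Scheduled CTs are at days 57, 113 and 197, each ±7 days (protocol Table 1 and section 6.5). The end-of-study contact is at day 227 (Table 1). 21 patients were enrolled (SAP section 6). The documents do not give the accrual dates, so first doses are assumed uniform over 1 October 2019 to 30 September 2020.

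**One patient.** First dose 10 March 2020, true progression 5 May 2020 (day 57).

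| Missing | Branch | Imputed date | Shift |
|---|---|---|---|
| Day | Start | 1 May | −4 days |
| Day | End, contact continuing | 31 May | +26 days |
| Day and month | Adverse-event start | 10 March (day 1) | −56 days |
| Day and month | Medication start | 1 January | 69 days before first dose |
| Day and month | End, contact assumed to stop 30 days after progression | 4 June | +30 days |

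**Negative DoR.** Now suppose 5 May was the response scan, and clinical progression followed later in May with the day unrecorded.

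- Start rule: 1 May − 5 May = −4 days.
- Only the year recorded, adverse-event start branch: 10 March − 5 May = −56 days.
- If the later event is a death instead, 1 May precedes a date on which the patient was known to be alive.

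**Range, day missing.** Applying the rules to every first-dose date and every event in the three scan windows:

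- Start rule: −30 to 0 days, mean about −15.
- End rule: 0 to +30 days, mean about +15.
- If the response is read as a start and the progression as an end, DoR can lengthen by up to 30 + 30 = 60 days. The longest scan-to-scan DoR is 204 − 50 = 154 days (nominally 197 − 57 = 140).

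Placement on the first-dose date cannot happen here for a scheduled scan. The earliest is day 50, 49 days after first dose, so always in a later calendar month. It would need an early clinical progression or death.

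**Range, day and month missing.** All shares are conditional on only the year being recorded.

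| Progression window | Adverse-event start: lands on first dose | Medication start: lands before first dose |
|---|---|---|
| C3D1 | 84.7% | 84.4% |
| C5D1 | 69.6% | 69.3% |
| C8D1 | 46.6% | 46.3% |

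The adverse-event branch moves the date by up to 203 days (day 204 to day 1). The end rule adds up to 30 days if contact stops 30 days after progression. If contact runs to day 227, it adds up to 227 − 50 = 177 days for a C3D1-window progression.

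**Undated events.** A progression with no date still counts in best overall response (SAP 10.5.4) and in the number progressing (10.5.5). It has no Kaplan-Meier time, and the censoring rule does not cover it.

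**The case against.** The strongest reply is that this will hardly ever operate. Response and progression are read from CT at fixed visits, protocol 12.1 requires entries to match source and missing data to be explained, and nothing in the documents points to any partial efficacy date. The study is single-arm and closed after stage 1. DoR is descriptive and listed per patient, and SAP 10.5 allows sparse endpoints to be reduced to basic summaries and listings. All of that stands, and it limits the weight of the point.

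A second reply is that the SAP is merely silent on which branch applies, so no wrong value is prescribed. The silence is real, but choosing a branch would not cure the problem. The start branches can put progression before response or before first dose. The end branches can put it well after it occurred.

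A third reply is that an earliest-possible-date convention would often give the same answer. This is correct for on-schedule scans with the day missing. The smallest gap between scheduled post-baseline scans is 56 − 14 = 42 days, longer than any month, so the earliest date after the last clean scan is still the 1st. The improvement comes from the bounds, not from preferring early dates.

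A reader might also infer more than the documents support:

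- **About two-thirds of patients would have a PFS of one day.** The average (84.7 + 69.6 + 46.6) / 3 = 67% applies only to progressions recorded by year alone, under the adverse-event start branch, with assumed uniform entry and equal weight on the three scans.
- **One wrong date would move the median among 21 patients.** DoR exists only for responders, whose number the documents do not give, and no such effect has been calculated.

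**Conclusion.** The point holds as a defect in the rule, with limited practical effect. Followed literally, SAP 9.3.2 can shift a progression, response or death by up to 30 days in a direction set by an unstated choice, and can make DoR negative. If the month is also missing, it can put progression on the first-dose date, or before it under the medication branch.

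The day-missing limits and the worked examples follow from the text and the calendar. The percentages rest on the assumed entry period and on only the year being known. The end-rule shifts rest on assumed last-contact dates. ORR and the stage 1 stopping decision use no imputed date. What is exposed is any individual PFS or DoR value with an incomplete date, and the descriptive summaries built on it.

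**What to change.** Replace the cross-reference in SAP 9.3.2 with an efficacy-date rule:

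- Use the date of the source scan, laboratory result or clinical assessment.
- If a progression date is still partial, impute one prespecified date within the reported month or year. It must fall after the latest of first dose, the last progression-free assessment and, for DoR, the documented response, and no later than last contact. The first-dose floor is needed because the baseline scan may precede first dose by up to 28 days.
- Hold a partial response date after first dose and before any later progression.
- Bound a partial death date below by the last date known alive.
- For a known event with no date, name one rule for its Kaplan-Meier time, for example the date of the visit at which it was recorded, with a sensitivity analysis at the other end of the interval.

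The cost is one SAP paragraph and minor programming. No new data are needed beyond source dates that sites should already hold. Where only the day is missing and scans were on schedule, the imputed date may still be the 1st of the month. The gain is one agreed rule and no impossible values.

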9.3.3 Missing dates for Primary Diagnosis/Prior therapy

Partial Primary diagnosis and prior therapy dates will have imputation performed as explained below for the purposes of calculation of relativity to study medication.

- If only Day is missing, impute the day 1
- If Day and Month are missing, impute the Month as January and the Day as 1.
- If the year of primary diagnosis is missing or the date of primary diagnosis is completely missing, then no date will be imputed.

10. Statistical Analysis

Due to early closure of the study, the analysis proposed in the SAP is based on the available data at the time of study closure.

The safety endpoints will be listed and/or summarized. No inferential statistical analyses will be performed.

Unless otherwise stated, all statistical analyses will be performed using a two-sided hypothesis test at the overall 5% level of significance.

When count data are presented, the percentage will be suppressed when the count is zero in order to draw attention to the non-zero counts. A row denoted "Missing" will be included in count tabulations where necessary to account for dropouts and missing patients. Unless otherwise specified, the denominator for percentages will be the number of patients with a non-missing assessment in a given treatment group within the analysis population of interest.

All statistical analyses will be performed using SAS 9.4 or higher.

10.1 Patient Disposition

A tabular presentation of the patient disposition data will be provided. It will include the number of patients screened, enrolled, assigned treatment, completed the treatment, as well as the number of dropouts, with reasons for discontinuation, number in each population sets, number of patients with dose reductions or interruptions (if applicable), etc. All patients' data will be used for this report.

10.2 Demographic and Baseline Characteristics

Analysis set: FAS

Demographic and baseline characteristics data will be summarized using descriptive statistics (n, mean, standard deviation, median, minimum, maximum) for continuous variables, and using frequencies and percentages for categorical variables.

Demographic characteristics will include age, race, gender, height, weight, etc.

Disease characteristics will include time from initial diagnosis to enrollment, chromosomal abnormalities, gene mutations, Rai staging at the time of screening, number of prior therapies, number of subject relapsed or refractory to the last therapy, time from date of last therapy to enrollment, ECOG performance status, etc.

10.3 Medical and Surgical History

Analysis set: FAS

This data will be summarized using frequencies and percentages by System Organ Class and Preferred Term. A listing will also be provided.

The medical history data will be coded using MedDRA dictionary [Version 23.0 (Hierarchy) or higher].

10.4 Prior and Concomitant Medications

Analysis set: FAS

Concomitant medications are those that were taken while on study drug. Also, the medications / non-drug treatments which start after study treatment will be termed as ‘Concomitant’.

Prior medications are those that were taken prior to the initial dose of study drug.

The medication data will be coded using WHO-Drug dictionary (WHODRUG GLOBAL B3 March 1, 2020 or higher) and the non-drug treatments data will be coded using MedDRA dictionary [Version 23.0 (Hierarchy) or higher].

A summary of frequencies and percentages by ATC level 2 and Preferred Terms and the listing of the prior and concomitant treatments taken will be provided.

10.5 Efficacy Analysis

Analysis Set: mITT and PP

- These analyses will be done for overall population. }

Note: The analyses outlined below are subject to availability of adequate data. In absence of adequate data, some of the efficacy endpoints discussed below will be presented with basic summaries and/or plots and listings, as appropriate.

10.5.1 Objective Response Rate (ORR)

It is defined as sum of CR and PR rates as defined by iwCLL guideline for CLL (Hallek et al. 2018)². Only those patients who have had a pre-treatment baseline efficacy evaluation and at least one post-treatment efficacy evaluation (that includes confirmed disease progression) will be considered evaluable for response. Overall ORR will be calculated.

Additionally, Disease Control Rate (DCR= CR+PR+SD) will be presented.

This data will be summarized using frequency, and percentage and the 95% CI (Using exact method based on binomial distribution, subject to availability of adequate data) for the Overall group.

The corresponding listing will also be provided.

10.5.2 Complete and Partial Response Rate

The investigator assessed response, which is done as per the iwCLL guideline for CLL will be used. Only those patients who have had a pre-treatment baseline efficacy evaluation and at least one post-treatment efficacy evaluation (that includes confirmed disease progression) will be considered evaluable for response.

This data will be summarized using frequency, and percentage. the 95% CI (Using exact method based on binomial distribution, subject to availability of adequate data) will be presented for the Overall only.

10.5.3 Duration of Response (DoR)

It is defined as the time when the measurement criteria are first met for PR or CR (whichever is reported first) until the date of documented disease progression or death. For subjects who neither progress nor die, the duration of response will be censored at the date of their last disease assessment.

This data will be summarized descriptively using n, mean, median, standard deviation, minimum and maximum values for overall subjects. The DoR data will be listed for each patient.

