10.5.5 Progression Free Survival (PFS)

It is defined as time of the first dose of Tenalisib to disease progression or death. Subjects who die without a reported prior progression will be considered to have progressed on the date of

their death. Subjects who did not progress or die will be censored on the date of their last tumor assessment that will be assessed at End of Treatment visit for this study. End of treatment visit will be considered as the cut-off visit for the calculation of PFS.

This data will be summarized using the Kaplan-Meier method and displayed graphically for overall subjects. The following reports will be generated:

- The Q1, median and Q3 PFS time will be provided along with 95% CI for the Q1, median, and Q3 PFS time will be presented for the Overall subjects using Brookmeyer-Crowley method, subjected to availability of adequate data.
- The number and % of patients with disease progression (further divided into disease progression or death) will be provided.
- The number and % of patients censored (further divided by reasons for censoring) will be provided.
- Kaplan-Meier curves will be produced.
- A listing of PFS data will be provided.

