10.6.7 ECOG

Analysis Set: Safety

ECOG performance status, as reported in the eCRF, will be summarized per cycle with number and percentage for each status category. This data will also be listed.

The baseline measurement is the last pre-treatment measurement taken on or before Cycle1 Day1.

11. Protocol Deviations

Analysis set: FAS

A full list of protocol deviations for the study report will be compiled prior to database closure. All deviations will be reviewed by the Medical monitor prior to database closure. Each deviation

will be categorized as major and minor and a decision will be taken by the medical monitor whether to include the subject in a PP analysis population set.

Protocol deviations will be presented as number and percentage of patients with minor and major deviations in the study. This data will also be listed as appropriate.

12. Listings

In addition to all the listings mentioned above, separate listings will be presented for the following:

- Screened patients
- Eligibility review
- Study completion/Reasons for withdrawal of patient from the study
- Analysis populations
- Prior therapy
- Baseline Serology assessment
- Cancer diagnosis
- Disease assessment at Screening visit
- Follow-Up Cancer Overall Assessment
- Study drug exposure
- Study drug accountability
- Target lesion assessment
- Non-target lesion assessment
- Disease Response assessment
- Overall tumor assessment
- Pregnancy test
- Investigator Comments
- Patient visits

13. References

2. Hallek, M. *et al.* iwCLL guidelines for diagnosis, indications for treatment, response assessment, and supportive management of CLL. *Blood*. 2018;131(25):2745-2760

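### Duration of response is censored by rule but summarised only by a plain mean, median and SD, with no event or censored counts

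*SAP*

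**What the plan says.** The primary objective (Protocol 2.1, SAP 3.1) rests on ORR and DoR together. SAP 9.3.2 treats DoR as a time-to-event variable: "For time-to-event endpoints (Progression Free Survival, Overall Response and Duration of response), if the date is completely missing, no imputation will be performed". SAP 10.5.3 gives the censoring rule: "For subjects who neither progress nor die, the duration of response will be censored at the date of their last disease assessment". The next paragraph gives the only planned summary: "This data will be summarized descriptively using n, mean, median, standard deviation, minimum and maximum values for overall subjects". A per-patient listing follows, with no censoring flag required.

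For PFS, SAP 10.5.5 plans "This data will be summarized using the Kaplan-Meier method and displayed graphically for overall subjects", with quartiles, Brookmeyer-Crowley intervals, event counts and "The number and % of patients censored (further divided by reasons for censoring) will be provided".

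Nothing else fills the gap. Protocol 8.1 repeats the DoR censoring rule, and Protocol 9.4.3 names DoR without a method. The general note in SAP 10.5 says "In absence of adequate data, some of the efficacy endpoints discussed below will be presented with basic summaries and/or plots and listings, as appropriate", but not how a censored value enters a basic summary.

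**The concern.** A censored duration is a lower bound. To compute a mean, median or SD, the programmer must either treat the response as having ended at the last assessment or drop the patient. The SAP does not choose, and both are biased. The reader of the DoR table could not tell how many responses were still ongoing.

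Censoring is built into this design. The study ends at C8D1 (Protocol 3.2), and patients considered for the compassionate use study have their end-of-study visit on that day (Protocol 6.9). A first response recorded at C8D1 and still ongoing has a duration of zero. For an endpoint in the primary objective, the reported figure could then say more about how early the response was first recorded than about how long it lasted.

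**Working it through.** The documents give no figure for DoR, so there is none to reproduce. They also give no responder count, response timing or assumed duration. Everything from step 2 on is therefore illustrative.

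**Step 1. Follow-up available by schedule.** Protocol Table 1 puts C3D1, C5D1, C8D1 and EOS at study days 57, 113, 197 and 227.
- From C3D1: 197 − 57 = 140 days. With the ±7-day scan windows: (197 + 7) − (57 − 7) = 154.
- From C5D1: 197 − 113 = 84 days.
- From C8D1: 197 − 197 = 0 days.

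This is not a hard cap. Protocol 6.7 allows later assessments, and a death by day 227 would give 227 − 57 = 170 days.

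**Step 2. Five invented responders** (not trial data): 56 (progressed), 140+, 140+, 84+, 0+ days. With censored values counted as complete, the mean is 420/5 = 84, the median 84 and the SD 59 days. Kaplan-Meier has one event with four at risk, so survival is 0.75 after day 56 and the median is not reached. The planned table would report 84 days although four of the five responses are ongoing.

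**Step 3. Expected value of the planned mean.** Assume T exponential with median m days, F(x) = 1 − 2^(−x/m), 1 month = 30.4375 days, first responses split 60/25/15% over C3D1/C5D1/C8D1, and censored values counted as complete.

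*Progression seen only at scheduled scans.* A C3D1 responder is recorded at 113 − 57 = 56 days if T ≤ 56 and otherwise at 140; a C5D1 responder at 84; a C8D1 responder at 0.

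Mean = 0.60·[56·F(56) + 140·(1 − F(56))] + 0.25·84 + 0.15·0
- m = 3 months (91.3 days): F(56) = 0.346, mean = 0.60·110.9 + 21 = 87.5 days = 2.9 months.
- m = 24 months (730.5 days): F(56) = 0.052, mean = 0.60·135.7 + 21 = 102.4 days = 3.4 months.

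*Progression seen the day it occurs.* Mean = (m/ln 2)·[0.60·F(140) + 0.25·F(84)]
- m = 3 months: 131.7·(0.60·0.654 + 0.25·0.471) = 67.3 days = 2.2 months.

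*Share censored* = 0.60·(1 − F(140)) + 0.25·(1 − F(84)) + 0.15.

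*True mean* = m/ln 2.

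| True median (months) | 3 | 6 | 12 | 24 |
|---|---|---|---|---|
| True mean (months) | 4.3 | 8.7 | 17.3 | 34.6 |
| Planned mean, seen at once | 2.2 | 2.7 | 3.1 | 3.2 |
| Planned mean, scheduled scans | 2.9 | 3.1 | 3.3 | 3.4 |
| Share censored | 49% | 68% | 82% | 91% |
| Kaplan-Meier at 140 days, scheduled scans | 0.326 | 0.570 | 0.755 | 0.869 |
| True share in response at 140 days | 0.346 | 0.588 | 0.767 | 0.876 |

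**Step 4. Sensitivity to response timing.** Planned mean in months, true median 3 to 24 months:
- All at C3D1: 2.8–3.6 to 4.3–4.5 (35% to 88% censored).
- 70/30/0: 2.6–3.4 to 3.8–3.9 (40% to 89%).
- 40/30/30: 1.7–2.3 to 2.5–2.6 (60% to 93%).

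**Step 5. Censored values dropped instead.** With the 60/25/15 split, the mean runs from 1.75–3.05 to 2.07–3.31 months. This choice is equally insensitive to the true duration.

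**The case against.** The strongest reply is that this SAP was written for a study already closed after stage 1 (SAP 5.1), with 21 patients enrolled and no clinically meaningful response. A descriptive summary of a few responders may be all that is feasible, and SAP 10.5 allows for sparse data. With so few patients, each responder's status could largely be reconstructed from the PFS counts and the Section 12 listings, such as "Disease Response assessment". The planned n, set against the number of responders, would show whether anyone had been dropped.

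Kaplan-Meier is no cure-all either. At a true median of 3 months (91 days), with the 60/25/15 split and scheduled scans, its survival is 0.756, 0.617 and 0.326 at days 56, 84 and 140. Its median is therefore 140 days, while the plain median, 84, is nearer the truth. If progression is seen the day it occurs, the order reverses: Kaplan-Meier gives 91 and the plain median 70. With five responders, the Kaplan-Meier median was not reached in 23%, 56–59%, 80–83% and 93–94% of simulated data sets at true medians of 3, 6, 12 and 24 months.

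These points limit the weight of the finding and the size of the remedy. They also qualify the link to the visit calendar: at a true median of 3 months, most values are events in three of the four splits. They do not justify a mean and SD over partly censored values without counts. Small numbers make that summary harder to read, and having to rebuild status from other outputs shows that the DoR summary is incomplete.

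**Conclusion.** The concern holds. SAP 10.5.3 defines a censored variable and plans a summary that ignores the censoring, for an endpoint in the primary objective that the SAP itself classes as time-to-event. Under the 60/25/15 assumption, an eightfold rise in true duration moves the planned mean by about 1.0 month (2.2 to 3.2) if progression is seen at once, or 0.5 month (2.9 to 3.4) with scheduled scans. The other splits tried show the same flatness. These sizes rest on assumed exponential durations and assumed response timing, so they indicate direction rather than predict this trial's result. The textual defect does not depend on them.

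The consequence is confined to correct reporting of DoR. No hypothesis, sample size or stopping rule uses it, and the number of responders is not given.

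**What to change.** At a minimum, add the numbers of events and censored responders to the DoR summary, and a censoring flag to the listing. Preferably, replace the descriptive sentence in SAP 10.5.3 with:

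> DoR will be summarised for responders by the Kaplan-Meier method, using the censoring rule in this section: number of responders, number of events (progression or death), number censored with reasons and, where data allow, Q1, median and Q3 with Brookmeyer-Crowley 95% CI and the curve. The DoR listing will flag censored values. If there are too few responders, individual durations will be listed with censored values marked +, and no mean or SD will be given.

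A bare cross-reference to 10.5.5 should be avoided, because that section carries a rule written for PFS: "End of treatment visit will be considered as the cut-off visit for the calculation of PFS". If the report states the follow-up limit, it should describe it as about 140 days by schedule from a first response at C3D1, or about 154 with visit windows.

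The cost is a few sentences. The method is already specified for PFS, and no new data are needed. The median may be reported as not reached; with the counts beside it, that is an accurate result.
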